#### 6.4 SAFETY VARIABLES

#### Pre-treatment adverse events

An AE will be classified as pre-treatment AE if it starts before the date/time of first randomized study medication intake (AE onset date/time < date/time of first randomized study medication intake).

1.0/30/10/2018 Page 14 of 28

# Treatment-emergent adverse event (TEAE)

An AE will be classified as a TEAE if it starts on or after the date/time of first randomized study medication intake (AE onset date/time  $\geq$  date/time of first randomized study medication intake).

In case of missing or incomplete dates/times not allowing a direct allocation to any of the two categories of AEs, a worst-case allocation will be done according to the available parts of the onset dates/times and the end dates. The AE will be allocated to the first category allowed by the available data, according to the following order:

- TEAE
- Pre-treatment.

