7. STUDY PROCEDURES

♦ Screening period (between Hours -24 to -1)

Within a maximum of 24 hours before administration of study medication (istaroxime or placebo), a medical screening will be performed on all prospective patients to assess suitability for the study. Prior to conducting any study specific procedures, the investigator or his/her designee will explain the study fully to the patient and provide him/her with a copy of the Patient Information Sheet and Informed Consent Document. If the patient is willing to participate in the study, s/he and the investigator or his/her designee will both sign the Informed Consent Document and a copy of the signed document will be kept by the patient.

1) Obtaining of ICF;

- 2) Evaluation of screening inclusion and exclusion criteria;
- 3) Stratification: Atrial fibrillation YES/NO;
- 4) Medical history, demographic/anthropometric data;
- 5) Alcohol and tobacco consumption patterns;
- Medication history (previous and concomitant), including a list of the patient's previous and current intake of vitamins, over-the-counter drugs and herbal products for the last 3 months. Chronic oral treatment with digoxin and other medications (e.g. diuretic and/or vasodilator) will also be recorded;
- 7) Vital signs (including body temperature and dyspnea);
- 8) 12-lead ECG; (Data obtained within 3 hours before the patient signed informed consent form can be accepted.)
- 9) Holter ECG;

- 10) Standard blood chemistry and Standard haematology;
- 11) TSH, T3 and T4;
- 12) Estimated glomerular filtration rate (eGFR);
- 13) Digoxin assay;
- 14) Urinalysis;
- 15) Alcohol breath test (at random, if deemed necessary by the Investigator/designee);
- 16) Serum pregnancy test (beta human chorionic gonadotropin [β-hCG]) for females of childbearing potential;
- 17) Echocardiography;
- 18) Serum creatinine clearance;
- 19) Human Immunodeficiency Virus, Hepatitis B and Hepatitis C tests;
- 20) Adverse events monitoring (after obtaining informed consent);
- 21) BNP, NT-proBNP and cTnT;

♦ Treatment period (Day 1)

- 1) Confirm eligibility;
- 2) Randomization of patients (after eligibility has been confirmed);
- 3) Insertion of multiple lumen intravenous catheter (or administration via peripheral vein);
- 4) Start istaroxime or placebo infusion (date and time of infusion start must be recorded in the CRF);
- 5) cTnT (at pre-dose in two samples, 3, 6, 12, 24, 48 and 72 hours after start of infusion);

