9. SAFETY ASSESSMENTS

- 1. AEs will be monitored throughout the study (i.e. from the time of signature of informed consent to treatment end + 30 days);
- 2. Physical examination (HF signs included) at screening, baseline, on study Day 4 or at discharge, and on study Day 30 during the follow up visit;
- 3. Vital signs (HR, BP, respiratory rate, body temperature and dyspnoea)) will be measured at screening, (concomitantly to hemodynamic measurements) during the pretreatment period, at 3, 6, 12, and 24 hours after infusion start, and then on study Day 3 and Day 4 or at discharge, and on study Day 30 during the follow up visit;
- 4. 12-lead ECG (HR, RR and PR intervals, QRS duration, QTc, rhythm, ectopy, ischemic changes) will be recorded and locally analyzed at screening and on study Day1, Day2, Day 3 and Day 4 or at discharge, and on study Day 30 during the follow up visit;
- 5. Continuous Holter monitoring will take place during screening, treatment (Day 1), and Day 2.
- 6. Blood samples will be collected and sent to the local laboratory during screening, 48 hours after infusion starts and on Day 30 to measure the following safety parameters:

Protocol N°: CVT-CV-002 42

- a) Hematology: red blood cell (RBC) count, Hb, hematocrit (Hct), white blood cell (WBC) count, differential WBC count, platelet count;
- b) Blood chemistry: electrolytes (Na⁺, K⁺, Ca⁺⁺, Cl⁻), albumin, total protein, glucose, creatinine, eGFR, BUN (blood urea nitrogen), alkaline phosphatase, ALAT, ASAT, total and conjugated bilirubin, gamma glutamyl transferase (γ-GT), total cholesterol, triglycerides;
- 7. Blood samples for creatinine will be collected by the local laboratory at each time after infusion start
- 8. cTnT or cTnI will be measured locally during screening. While cTnT only will be measured by the central laboratory, at pre-dose in two samples, at 3, 6, 12, 24, 48, 72 hours after infusion start or at discharge and at 30days by using the hs test from Roche cobas. Incidence of cTnT elevation (>50% or > 20% relative increase over the basal cTnT levels at baseline, for patients with cTnT levels at baseline < or ≥ of the 99% URL (upper reference levels, as defined for the Roche hs test, in patients with normal renal function, eGFR ≥85 ml/min); in patients with eGFR below this value, the renal function variations must be considered in evaluating the significance of the cTnT changes).

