10. REPORTING OF ADVERSE EVENTS

10.1 Definition of Adverse Event (AE)

Adverse event (AE) is an adverse medical event that occurs following informed consent signature, the event is not necessarily related to the treatment. Therefore, adverse events may be any discomfort and unconscious signs (such as abnormal laboratory examination results), symptoms or illnesses.

- Any adverse event, whether serious or not, whether related to the treatment or not, should be recorded on the CRF.
- Investigator should follow up the patients that dropped out because of any adverse event until recovery, and record the date of AE occurring and recovering.
- If during adverse event follow-up, the adverse event progresses to an "SAE", or if a subject experiences a new SAE whose relationship to the study drug(s) cannot be ruled out, the investigator must immediately report the information to the sponsor.

Protocol N°: CVT-CV-002

Even if the subject does not return to normal or to his or her previous state, the follow-up can be considered finished when the following procedures have been taken:

- The investigator judges that the follow-up of the subject concerned is no longer necessary based on the progress made during the follow-up,
- The reason for such a judgment is entered as a comment on the case report form for the follow-up.

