### Adverse events

Pre-treatment AEs and TEAEs will be presented separately. Pre-treatment AEs will be presented in the listings only.

The number of treatment-emergent AEs, SAEs, ADRs, AEs leading to discontinuation and AEs leading to death, and the number and the percentage of patients experiencing treatment-emergent AEs, SAEs, ADRs, AEs leading to discontinuation and AEs leading to death will be summarised by treatment group.

AEs will be coded using the MedDRA dictionary (version 16.0). The SOCs and PTs will be used for tabulation. The number of AEs and the number and the percentage of patients with at least one AE will be presented by SOC and PT for treatment-emergent AEs, SAEs, ADRs, AEs leading to discontinuation and AEs leading to death by treatment group.

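### The SAP defines treatment-emergent AEs by onset time alone, so an AE that starts between consent and infusion and then worsens, becomes serious, stops the drug or turns fatal is missing from every AE table unless sites enter the worsening as a new AE

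*SAP*

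**What the plan says.** SAP 6.4 has two classes of AE, separated by one timestamp. For the first, "An AE will be classified as pre-treatment AE if it starts before the date/time of first randomized study medication intake"; for the second, "An AE will be classified as a TEAE if it starts on or after the date/time of first randomized study medication intake". Neither definition mentions a change in severity, a change to serious, or a fatal outcome after dosing. Where onset is missing or incomplete, the AE goes to the treatment-emergent class if the available data allow it.

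SAP 7.8 (Adverse events) then states: "Pre-treatment AEs will be presented in the listings only". The tables it plans cover "The number of treatment-emergent AEs, SAEs, ADRs, AEs leading to discontinuation and AEs leading to death", with matching patient counts and percentages and breakdowns by system organ class and preferred term.

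Collection starts before dosing. Protocol 10.1 says "Adverse event (AE) is an adverse medical event that occurs following informed consent signature". Protocol 9 gives the monitoring period as "from the time of signature of informed consent to treatment end + 30 days". Protocol 7 limits the interval before dosing: "Within a maximum of 24 hours before administration of study medication (istaroxime or placebo), a medical screening will be performed".

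Protocol 10.1 also foresees that an event may change after it has been recorded: "If during adverse event follow-up, the adverse event progresses to an" SAE, the investigator must report it to the sponsor at once. The available text does not say whether the change gets its own record or onset time.

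**The concern.** Safety and tolerability are stated objectives of this trial, and each dose is given to only 40 patients. The patients are acutely decompensated and need i.v. diuretics, so new events in the hours before the infusion are plausible. If such an event gets worse during the infusion, the worsening happens on treatment, but the table rule looks only at when the event began.

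The rule also cuts across the SAP's own definitions. In SAP 6.4 an AE leading to discontinuation is defined by the action taken, and an AE leading to death by its outcome. An AE that starts an hour before the infusion and then causes the study drug to be stopped meets the discontinuation definition, yet its onset time removes it from the discontinuation table. A fatal AE is lost from the death table in the same way.

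Protocol 14.2 summarises AEs, ADRs, SAEs and AEs leading to withdrawal without restricting them to treatment-emergent events. SAP 1.1, which lists changes from the protocol, mentions only the echocardiographic analyses.

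**Working it through.** The documents give no figure to reproduce. The check sets the rules side by side and then works out a per-patient scale.

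**1. Can the event exist?** Yes. AEs count from consent (Protocol 9 and 10.1), and screening may run up to 24 hours before study drug (Protocol 7). A dosed patient can therefore have an AE with a known onset before infusion start.

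**2. How is it classed if it later worsens?** As pre-treatment. The SAP 6.4 test uses onset only, so later severity, seriousness, action taken and outcome do not move the record.

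**3. Which tables lose it?** The SAP 7.8 sentence listing the tables could be read as attaching treatment-emergent to the first item only, leaving SAEs, ADRs, discontinuations and deaths unrestricted. The listings-only sentence for pre-treatment AEs rules that out. The overall, SAE, ADR, discontinuation and death tables all omit the event.

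**4. Which summaries do not use the classification?**

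| Summary in SAP 7.8 | Depends on AE onset? |
|---|---|
| Vital signs, as change from pre-dose | No |
| cTnT and cTnT elevation | No |
| Holter, at screening and Days 1 and 2 | No |
| 12-lead ECG | No |
| Laboratory shift tables | No |
| Potassium and renal function | No |
| AE, SAE, ADR, discontinuation and death tables | Yes |

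Day-30 mortality is a safety endpoint in SAP 3.2.2 and Protocol 6.2, and Protocol 14.2 says it will be summarised by group. SAP 7.8 describes no such summary, so the only death table it spells out is the treatment-emergent one.

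**5. Is there a rule that brings the worsened event back?** None in the available text. SAP 6.4 (Count of adverse events) counts two records with the same preferred term as two events. That would accommodate a new line on worsening but does not require one.

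**6. Scale.** SAP 4.0 gives 40 patients per istaroxime dose and 20 placebo patients per cohort. SAP 7.4 pools placebo for everything except echocardiography, so placebo is 20 + 20 = 40. If all randomised patients are dosed, one omitted patient changes a group percentage by 1/40 = 2.5 points, in any of the three groups. The total effect is the number of such patients times 2.5 points, and the documents give no basis for that number.

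**The case against.** The case for leaving the rule alone has real weight.

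- **The exposed set is narrow.** It covers new events with a known onset in at most about 24 hours. A condition present before consent is not yet an AE; if it worsens on drug, the AE begins at the worsening and is treatment-emergent. Unclear onset times already default to treatment-emergent. Protocol 4 requires eligibility just before randomisation as well as at admission, so marked hypotension or low potassium in screening should largely keep a patient out.
- **Much of the signal shows elsewhere.** Worsening ectopy appears in the Holter summary, a fall in blood pressure in vital signs, and a fall in potassium in the renal table. These do not show seriousness, relatedness or drug withdrawal, however, and nausea and vomiting have no parallel summary.
- **Recording practice may close the gap.** If sites enter a worsening as a new AE, nothing is lost. Protocol 10.5 and the CRF instructions are not available here, so this cannot be settled. The line quoted from Protocol 10.1 concerns prompt reporting to the sponsor, not how onset is recorded.
- **The rule is the same in all blinded arms,** and the events remain in the listings. Neither the primary endpoint nor the cTnT interim analysis is touched.

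These points limit the consequence. They do not change what SAP 6.4 and 7.8 do with a single record that has a known pre-infusion onset.

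A reader might infer three stronger things. The first is that such events vanish from every safety table; the table in the working shows they vanish from the AE tables only. The second is that the rule favours istaroxime. It can only lower counts, but it does so in every arm, and bias towards the drug would need istaroxime to worsen such events more often than placebo, for which the documents give no data. The third is that one placebo patient is worth 1/20 = 5 points. That holds for a single cohort's placebo arm, and no planned AE table uses that denominator.

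**Conclusion.** The point holds for the AE tables. A single AE record with a known onset between consent and infusion start stays out of all five types of AE table in SAP 7.8, whatever happens to it after dosing begins. The size is about 2.5 percentage points per omitted patient in any group; the total effect and the direction of any bias are unknown.

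This rests on two assumptions: that sites do not open a new AE record when an event worsens, and that about 40 patients per group are dosed. The first cannot be checked from the available text, and a SAP definition should not depend on it. The missing mortality summary in SAP 7.8 adds to the problem, because it leaves the onset-restricted table as the only specified account of deaths.

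The gap is worth closing before unblinding. It does not put the safety evaluation as a whole in doubt.

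**What to change.** **SAP 6.4.** Extend the treatment-emergent definition to an AE that started before first study drug and, on or after it, increased in severity, became serious, led to study-drug withdrawal or had a fatal outcome. Apply this to all AE tables in SAP 7.8.

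**Dating the change.** The action-taken and outcome fields already used in SAP 6.4 support the discontinuation and fatal categories without new data. The safety population contains only dosed patients, so withdrawal of study drug or death must follow infusion start. For severity and seriousness, use the recorded date of change or a new AE line where one exists. Where the timing cannot be established, allocate to treatment-emergent, extending the worst-case rule SAP 6.4 already applies to incomplete onset times. An AE known to have ended before the infusion stays pre-treatment.

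**SAP 7.8.** Add a Day-30 mortality summary by treatment group that does not depend on AE onset.

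**SAP 1.1.** Record that the AE tables are restricted to treatment-emergent events, since Protocol 14.2 has no such restriction.

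**Cost.** A wording change and a little extra programming. The worst-case allocation will over-count some events that did not change after dosing. Dates of worsening may not exist for patients already treated, and asking sites for them would be new data collection.

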# Serious adverse event (SAE)

A SAE is an AE judged as serious.

# Adverse drug reaction (ADR)

An ADR is an AE judged as "Certainly related", "Possibly related", "Possibly unrelated", "Uncertain".

# Adverse event leading to discontinuation

An AE leading to discontinuation is an AE with action taken equal to "Study drug withdrawn and/or patient withdrawn from the study".

# Adverse event leading to death

An AE leading to discontinuation is an AE with outcome equal to "Fatal".

# Count of adverse events

Two AEs with the same Preferred Term (PT) and classified in the same category (pretreatment AE or TEAE) will be considered as two different events when calculating the "number of events" in the tables.

# Incidence of cTnT elevation relative

Percent change from baseline in cTnT will be calculated using the following formula at all post-dose timepoints (3h, 6h, 12h, 24h, 48h, 72h):

% change from baseline = 100 \* (cTnt at timepoint – cTnT at screening) / cTnT at screening

The following categories will be defined at each timepoint:

- For patients with normal cTnT value (< URL) at screening:
  - A patient will be classified as a "patient with a percent change from baseline in cTnT >50%" if the percent change from baseline in cTnT is greater than 50% (percent change from baseline in cTnT > 50%);
- For patients with abnormal cTnT value ( $\geq$  URL) at screening:

1.0/30/10/2018 Page 15 of 28

A patient will be classified as a "patient with a percent change from baseline in cTnT >20%" if the percent change from baseline in cTnT is greater than 20% (percent change from baseline in cTnT > 20%);

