# The safety endpoints are:

- Incidence of Adverse Events (AEs);
- Change in vital signs;
- Change in 12-lead Electrocardiogram (ECG) parameters;
- Incidence of clinically or hemodynamically significant episodes of supraventricular or ventricular arrhythmias detected by continuous ECG dynamic monitoring;
- Change in laboratory parameters (hematology, blood chemistry and urinalysis);
- Change in renal function (Estimated glomerular filtration rate (eGFR));
- Change in cTnT;
- Incidence of cTnT elevation relative (>50% or >20% relative increase over the cTnT levels at baseline, for patients with cTnT basal levels at baseline < or ≥ of the 99% Upper Reference Limit (URL, as defined for the Roche hs test to be 14 ng/L) respectively;
- Mortality at Day 30.

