#### 6.5 BASELINE

The baseline used in the analysis for each variable (for which comparison with baseline is requested) is reported in the table below:

Endpoint	Baseline
Laboratory parameters, renal function	Screening
Echocardiographic parameters, VAS	Pre-dose Day 1
score for dyspnoea, vital signs	
BNP, cTnT	Mean (pre-dose 1, pre-dose 2) at Day 1

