# 7.0 STATISTICAL METHODOLOGY

## 7.1 HANDLING OF MISSING DATA

The number of patients with missing data will be presented under the "Missing" category, if present. Missing values will be included in the denominator count when computing percentages.

When continuous data are being summarised, only the non-missing values will be evaluated for computing summary statistics.

Missing or incomplete data will be treated as described in sections 6.1, 6.3 and 6.4.

There will be no imputation of missing echocardiographic data.

Other critical missing data will be discussed prior to treatment unblinding, if any. Decisions will be taken during the blind review of the data and will be fully documented in the Data Review Report.

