### 7.2 COVARIATES AND SUBGROUPS

Linear Mixed Models for Repeated Measures (MMRM) will include treatment, centre, timepoint, gender, baseline cTnT (normal <URL, abnormal ≥URL), atrial fibrillation (Yes/No) and treatment\*timepoint interaction as fixed effects and baseline and baseline\*timepoint interaction as covariates.

Analysis of Covariance (ANCOVA) models will include treatment, centre, gender, baseline cTnT (normal <URL, abnormal ≥URL) and atrial fibrillation (Yes/No) as fixed effects and baseline as covariate.

ANOVA models for echocardiographic parameters will include treatment only. For analysis of Cohort 1, treatment is defined as (0.5 µg/kg/min dose, placebo). For analysis of Cohort 2, treatment is defined as (1.0 µg/kg/min dose, placebo).

All baseline values considered in the statistical analyses have been defined in the paragraph 6.6.

1.0/30/10/2018 Page 16 of 28

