# 7.3 INTERIM ANALYSIS AND SEQUENTIALITY OF ANALYSES

After the completion of cohort I, a safety interim analysis will be performed and the Data Monitoring Committee (DMC) members will evaluate the incidence of cTnT elevation. At interim analysis, the DMC may recommend to do not proceed with the next cohort if the incidence of cTnT elevation is found to be statistically significantly higher on the istaroxime dose than on placebo, or if this difference is deemed to be clinically relevant. Consequently, the clinical study will be prematurely terminated.

Randomization data and datasets needed to conduct the interim analysis will be given by an independent statistician to the DMC statistician. The DMC will be unblinded when performing the interim analysis.

During the interim analysis, DMC members will analyze and discuss the results in closed sessions. The DMC is required to keep confidential and undisclosed until study conclusion: i) these discussions, ii) the detailed minutes thereof, and iii) the interim analysis results.

For the primary endpoint, the primary comparison will be  $0.5 \mu g/kg/min$  dose of istaroxime versus placebo at 24 hours. Highest dose of istaroxime (1.0  $\mu g/kg/min$ ) versus placebo will be tested as a secondary comparison.

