# **Biomarkers**

NT-proBNP and cTNT and increase of cTnT will be summarised by treatment group at screening visit and at all timepoints during the study by means of descriptive statistics.

The number and percentage of patients with a percent change from pre-dose in cTnT >50% and >20% will be summarized at each post-dose timepoints by treatment group.

The number and percentage of patients with a normal cTnT value (<14 ng/L) at screening and with a percent change from pre-dose in cTnT >50% and the number and percentage of patients with an abnormal value of cTnT (≥14 ng/L) at screening and with a percent change from pre-dose in cTnT >20% will also be summarized at each post-dose timepoints by treatment group.

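### SAP 6.4 computes cTnT elevation from the screening value, against the pre-dose baseline in SAP 6.5, and SAP 6.4 and 7.8 set the threshold by screening where SAP 3.2.2 uses baseline

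*SAP*

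**What the plan says.** The SAP describes the incidence of cTnT elevation in four places.

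- **SAP 3.2.2, safety endpoints:** a rise of more than 50% or more than 20%, defined as "relative increase over the cTnT levels at baseline, for patients with cTnT basal levels at baseline" below, or at or above, the 99% URL (14 ng/L on the Roche hs test). Both the reference value and the threshold come from baseline. Protocol 6.2 words it the same way.
- **SAP 6.4, the derivation:** labelled percent change from baseline at 3, 6, 12, 24, 48 and 72 hours, but computed with "cTnT at screening) / cTnT at screening". The threshold is chosen by screening cTnT.
- **SAP 6.5, the baseline table:** for BNP and cTnT, "Mean (pre-dose 1, pre-dose 2) at Day 1". Its screening row covers only laboratory parameters and renal function.
- **SAP 7.8, Biomarkers:** counts patients "with a normal cTnT value (<14 ng/L) at screening and with a percent change from pre-dose in cTnT >50"%, and the matching group at or above 14 ng/L with a rise above 20%. The change is from pre-dose, but the threshold is set by screening.

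On the assays, Protocol 9 says "cTnT or cTnI will be measured locally during screening. While cTnT only will be measured by the central laboratory" from pre-dose onward, using the Roche hs test. SAP 7.2 adds "All baseline values considered in the statistical analyses have been defined in the paragraph 6.6", but section 6 ends at 6.5. SAP 1.1 lists only echocardiographic changes from the protocol, so none of this is a declared change.

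**The concern.** Two things conflict: the value from which the rise is measured, and the value that decides whether 50% or 20% applies. On the first, 6.4 stands alone against 3.2.2, 6.5 and 7.8. On the second, 6.4 and 7.8 stand against 3.2.2 and the protocol.

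Screening is not a harmless synonym for baseline. It may be up to 24 hours before dosing (Protocol 7), and its troponin may come from a different laboratory or assay. Coded as written, 6.4 can divide a central hs-cTnT result by a local one and apply the Roche 14 ng/L limit to a local value. It gives no result for a patient with local cTnI only. SAP 7.1 says "Missing values will be included in the denominator count when computing percentages", so such a patient would still sit in the denominator and lower the reported incidence.

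The endpoint carries weight. After Cohort I the DMC "members will evaluate the incidence of cTnT elevation" and may advise against the next cohort. SAP 7.3 does not say which definition it uses.

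**Working it through.** The documents give no incidence, power or event count for cTnT elevation, so there is no plan figure to reproduce. The check applies the written rules to the same values.

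**Rules** (scr = screening, pre = mean of the two pre-dose samples, post = a post-dose value; threshold 50% if the stratum value is below 14 ng/L, otherwise 20%):

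- 6.4: 100 × (post − scr)/scr, threshold by scr
- 7.8: 100 × (post − pre)/pre, threshold by scr
- Baseline definition (3.2.2 read with 6.5): 100 × (post − pre)/pre, threshold by pre

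**Worked cases** (chosen values, ng/L):

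| scr / pre / post | 6.4 | 7.8 | Baseline definition |
|---|---|---|---|
| 20 / 26 / 27 | 7/20 = +35.0% v 20: elevated | 1/26 = +3.8% v 20: no | +3.8% v 20: no |
| 30 / 20 / 26 | −4/30 = −13.3% v 20: no | 6/20 = +30.0% v 20: elevated | +30.0% v 20: elevated |
| 13 / 15 / 19 | 6/13 = +46.2% v 50: no | 4/15 = +26.7% v 50: no | +26.7% v 20: elevated |
| 15 / 13 / 17 | 2/15 = +13.3% v 20: no | 4/13 = +30.8% v 20: elevated | +30.8% v 50: no |

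The first two rows show the reference-value conflict and the last two the threshold conflict.

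**Flip points** (exact, for screening and pre-dose values of at least 14 ng/L):

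- No change from pre-dose (post = pre): 6.4 flags the patient when pre/scr > 1.20.
- A 30% rise (post = 1.3 × pre): 6.4 misses it when 1.3 × pre/scr ≤ 1.2, that is scr/pre ≥ 1.3/1.2 = 1.083.

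**How often the rules disagree** (simulation with no drug effect, one timepoint). Assumed: log-normal cTnT with median 25 ng/L and log SD 0.7, within-patient CV 10% or 20%, and a pre-dose to screening ratio of 0.8 to 1.2.

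- Classed as elevated: 0.1% to 43.3% by 6.4, 5.1% to 17.9% by 7.8, and 4.3% to 18.4% by the baseline definition.
- 6.4 and the baseline definition disagree for 4.3% to 36.0% of patients.
- 7.8 and the baseline definition disagree for 0.3% to 2.5%.

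**Effect on the between-arm difference** (second simulation, one threshold applied to everyone). Assumed: central log SD 0.10, extra screening log SD 0.1 to 0.4, screening-to-pre-dose drift −0.1 to +0.1 log units, and a median rise of 30% with log SD 0.2 on istaroxime.

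| Threshold | Placebo rate, 6.5 | Placebo rate, 6.4 | Difference, 6.5 | Difference, 6.4 |
|---|---|---|---|---|
| >20% | 6.6% | 5.2% to 42.3% | 56.4 points | 22.7 to 47.2 points |
| >50% | 0.0% | 0.2% to 23.5% | 26.7 points | 17.8 to 39.7 points |

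With no extra screening variability and no drift, 6.4 at >20% gives a placebo rate of 9.9% and a difference of 53.0 points. With no extra variability and drift of ±0.1, the difference is 44.5 to 48.8 points. All SDs, the drift and the drug effect are assumptions.

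**The case against.** The best defence is that the SAP already says which baseline governs. SAP 6.5 names cTnT, and 7.8, which specifies the reported summaries, uses change from pre-dose throughout. SAP 7.8 also plans counts above 50% and above 20% with no screening stratum, and those are free of both conflicts. Harm from the formula therefore arises only if 6.4 is what gets programmed. This is fair, and it confirms 6.4 as the outlier. But 6.4 is the only derivation printed under the endpoint's own heading, and following 7.8 instead still uses a stratum that 3.2.2 does not.

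Other points stand in part:

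- The threshold conflict is much the smaller of the two (0.3% to 2.5% against 4.3% to 36.0% in the simulation) and needs values that straddle 14 ng/L.
- The protocol says only at baseline; the pre-dose meaning comes from SAP 6.5.
- Protocol 7 lists cTnT at screening, so whether any patient has local cTnI only is unknown.
- The DMC may act on clinical relevance as well as on significance, so no mechanical rule turns on 6.4.
- The simulations rest on assumed inputs. The conclusion rests on the text and the flip points.
- The table mock-ups are in a separate document that was not available and may settle which rule is programmed.

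**Conclusion.** The concern holds. SAP 6.4 contradicts its own label, SAP 6.5 and SAP 7.8 on the reference value. SAP 6.4 and 7.8 contradict SAP 3.2.2 and Protocol 6.2 on the stratum. The 6.6 in SAP 7.2 is probably a numbering slip.

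If 6.4 is programmed, individual classifications change at modest shifts between screening and pre-dose: more than 20% one way creates an elevation where nothing changed, and 8.3% the other way hides a 30% rise. Both samples precede dosing, so the error acts on both arms alike and chiefly distorts the incidences. Its effect on the istaroxime–placebo difference depends on the threshold, the drift and the assay variability, none of which the documents give. In the settings tried, the difference shrank every time at >20% and moved either way at >50%. This should be fixed, since it is a listed safety endpoint that the DMC reviews. It does not bear on the primary efficacy analysis.

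**What to change.** 1. In SAP 6.4, replace the screening value by the 6.5 baseline (the mean of the two central pre-dose hs-cTnT samples), both in the formula and in the split at 14 ng/L.
2. Use the same baseline stratum in SAP 7.8.
3. Correct the cross-reference in SAP 7.2 from 6.6 to 6.5.
4. State in SAP 7.3 that this definition applies to the DMC review. If the Cohort I review has been done, report which rule it used and show the result under the corrected rule.
5. Preferably, add a rule for missing pre-dose samples: use the single sample if one is missing. If both are missing, show the patient as missing under SAP 7.1 and also report incidence among evaluable patients.

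The cost is SAP wording and one derived-variable specification. Both pre-dose samples are already scheduled, so no new data are needed.
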